8.4.3 Secondary Analysis (or Analysis of Secondary Endpoints)

The study will use descriptive statistics to report on the safety/toxicity and efficacy of pre-operative pembrolizumab-based treatment, including adverse events by NCI CTCAE (v 5.0) criteria and perioperative complications; pathologic response; R0 resection rate; and 2-year RFS. The sample size of each cohort will be too small to compare these results to historic data (i.e. from the Nordlinger EORTC study). However, we would consider the approach feasible if (1) ≥ 14 of 17 patients ($\geq 83\%$) are able to successfully undergo R0 resection within 6 weeks of last chemotherapy administration (if applicable); and (2) the rate of serious postoperative complications attributable to pembrolizumab-based treatment does not exceed 33% (6 of 17 patients).

The study will also use descriptive statistics to compare 2-year RFS rates in patients who do or do not receive adjuvant pembrolizumab-based therapy.

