Principal Investigator

Site

Printed Name

Signature

Date

[figure not shown]
Abstract

Title	A Phase 2 Study of Preoperative Immunotherapy in Patients with Colorectal Cancer and Resectable Hepatic Metastases
Patient population	Patients with colorectal cancer (CRC) with liver-dominant or liver-only metastases who have received prior 5-fluorouracil (5-FU), leucovorin, and oxaliplatin (FOLFOX) chemotherapy and are appropriate candidates for resection of liver metastases.
Rationale for Study	We hypothesize that pembrolizumab plus vactosertib will increase tumor-infiltrating lymphocytes (TILs) and promote response without increasing perioperative complications.
Primary Objective	To characterize the change in the populations of TILs induced by neoadjuvant pembrolizumab plus vactosertib in patients with metastatic CRC.
Secondary Objectives	
To establish the safety/toxicity profile of pembrolizumab-based treatment in the perioperative setting for patients with CRC with potentially resectable hepatic metastases, including rates of perioperative complications.
 
To explore the efficacy of this strategy in this patient population. Clinical outcome measures will include response to pembrolizumab plus vactosertib as measured by R0 resection rate; pathologic response; and 1-year and 2-year relapse-free survival (RFS).

Study Design	Phase 2, single-site, open-label prospective clinical trial. See schema below. Additional cohorts exploring novel pembrolizumab-based combinations during this same perioperative window (e.g., pembrolizumab in combination with other immuno- or molecularly targeted agents, following FOLFOX) may be added and enrolled to in sequential fashion via a protocol amendment.
Number of patients	Up to 19 patients will be enrolled in the initial cohort (17 evaluable patients with paired pre-treatment biopsy and post-pembrolizumab plus vactosertib analyzable tumor specimens).
Duration of Therapy	Patients will receive a single cycle of pembrolizumab plus vactosertib prior to planned hepatic metastasectomy. Additionally, up to 8 cycles of adjuvant pembrolizumab plus vactosertib may be administered after hepatic metastasectomy.
Duration of Follow up	Patients will be followed for up to 1 year after the last dose of pembrolizumab is administered or 2 years after surgery (whichever is longer).
Duration of study	The study will reach completion 3 years from the time the study opens to accrual.

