3.1 Characteristics

This is a single arm, open-label trial evaluating the feasibility, immune effects, safety, and efficacy of pembrolizumab-based treatment in the preoperative setting for patients with CRC undergoing planned liver resection for hepatic metastases. The primary endpoint is the proportion of patients with a ≥ 2 -fold increase in the number of TILs in post- vs. pre-pembrolizumab-based treatment tumor specimens.

Based on the results of this initial cohort, this trial may be subsequently amended to explore other novel pembrolizumab-based combinations (such as pembrolizumab in combination with another IO agent, chemotherapeutic, or a molecularly targeted agent that potentiates the efficacy of pembrolizumab) that will be decided by the Joint Steering Committee (JSC). Each of these new cohorts will be tested and enrolled to in sequential, non-randomized fashion. The trial is not designed to compare arms.

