3.2 Number of Patients

In order to accrue 17 patients who are evaluable for the primary endpoint, the plan is to enroll a total of 19 patients. If 2 or more of first 6 patients are unable to undergo planned surgical resection of their liver metastases in timely fashion (i.e., within 4-6 weeks of the final chemotherapy administration [if applicable]) or experience surgical complications attributed to pembrolizumab-based treatment, accrual will be suspended, and our strategy will be revisited.

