8.2 Determination of Sample Size and Accrual Rate**8.2.1 Sample Size and Power Estimate**

For the primary objective, there will be a binary classification (28). A patient will be considered to have a “positive response” if there is a ≥ 2 -fold increase (from pre- to post-treatment) in the number of TILs, and a “negative response” if there is < 2 -fold increase. Obtaining paired specimens from 17 patients will be sufficient to determine whether 40% or more achieve a “positive response,” compared to a null hypothesis of 10% or less. This comparison has a power of 0.91 at a significance level of 0.05 for a directional binomial test.

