8.2.2 Replacement Policy

We plan to enroll 19 patients to achieve our goal of 17 patients evaluable for the primary study outcome. If more than 2 patients turn out not to be evaluable for the primary study outcome (i.e., do not have available post-pembrolizumab-based neoadjuvant treatment tumor tissue available for analysis), they may be replaced upon discussion with the study Principal Investigator and JSC.

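### Both whole-cohort feasibility cut-offs in section 8.4.3 contradict their own percentages (14/17 is 82.4%, not at least 83%; 6/17 is 35.3%, above 33%), and no analysis population is named for them

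*Combined protocol and SAP*

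**What the plan says.** Section 3.1 describes the study in these terms: "This is a single arm, open-label trial evaluating the feasibility, immune effects, safety, and efficacy of pembrolizumab-based treatment in the preoperative setting". The only numeric feasibility criterion for the whole cohort is in section 8.4.3, which introduces two conditions with "we would consider the approach feasible if":

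1. At least 14 of 17 patients, with at least 83% in parentheses, "are able to successfully undergo R0 resection within 6 weeks of last chemotherapy administration (if applicable").
2. "the rate of serious postoperative complications attributable to pembrolizumab-based treatment does not exceed 33% (6 of 17 patients").

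Section 8.4.3 names no analysis set for either condition. Elsewhere 17 is the target number for the primary endpoint:

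- The Abstract speaks of "17 evaluable patients with paired pre-treatment biopsy and post-pembrolizumab plus vactosertib analyzable tumor specimens".
- Section 3.2 says "In order to accrue 17 patients who are evaluable for the primary endpoint, the plan is to enroll a total of 19 patients".
- Section 8.2.1 says "Obtaining paired specimens from 17 patients will be sufficient".
- Section 8.2.2 describes the non-evaluable patients as those who "do not have available post-pembrolizumab-based neoadjuvant treatment tumor tissue available for analysis".

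Section 8.4.1 assigns the R0 rate to patients who are resected, and safety to all patients who received at least one dose. Neither set is fixed at 17.

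**The concern.** Each condition states one threshold in two ways, and the two ways disagree by one patient. In both conditions the count is the more lenient form. At a borderline result the feasibility verdict depends on which form is read, and that choice could be made after the data are known.

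The unnamed denominator adds a second ambiguity. Suppose the 17 are the patients with paired specimens. An unresected patient with a usable second biopsy (section 6.1.4) then stays in and counts as a resection failure. An unresected patient without one leaves the 17 and does not count as a failure. Under section 8.2.2 such a patient may be replaced once more than 2 are not evaluable. If instead the denominator is resected patients, as section 8.4.1 has it for the R0 rate, nobody who missed surgery counts against a criterion about reaching R0 resection in time.

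At stake is the feasibility statement for the cohort. The rules for the first six patients (sections 3.2, 5.1.4 and 8.3) are separate.

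**Working it through.** **Inputs.** From section 8.4.3: 14 of 17 with 83%, and 6 of 17 with 33%. From section 3.2: 19 to be enrolled. The documents give no expected rate for timely R0 resection or for serious attributable complications, so the true rates below are assumptions shown as a range.

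**Step 1: reproduce the stated percentages.**

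- 14/17 = 82.4%, below 83%.
- 6/17 = 35.3%, above 33%.

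Neither is reproduced. Rounding to a whole percent gives 82% and 35%, and no count out of 17 rounds to 83% or 33%.

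**Step 2: find the counts that the percentages imply.**

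- 0.83 × 17 = 14.11, so at least 15 are needed (15/17 = 88.2%).
- 0.33 × 17 = 5.61, so at most 5 are allowed (5/17 = 29.4%).

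**Step 3: try other denominators.** For n from 15 to 21, only n = 18 has counts that round to both percentages (15/18 = 83.3%, 6/18 = 33.3%). The documents name no set of 18. With 19 treated patients, 83% needs 16 (0.83 × 19 = 15.77) and 33% allows 6 (6/19 = 31.6%). The boundary counts therefore depend on the denominator.

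**Step 4: size for condition 1.** With X binomial, n = 17 and true rate p, the chance of meeting a cut-off k is P(X ≥ k) = Σ C(17, j) p^j (1 − p)^(17 − j), summed over j = k to 17.

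| Assumed R0 rate | P(X ≥ 14) | P(X ≥ 15) | Difference = P(X = 14) |
|---|---|---|---|
| 80% | 0.549 | 0.310 | 0.239 |
| 83% | 0.675 | 0.429 | 0.246 |
| 90% | 0.917 | 0.762 | 0.156 |

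The nearest figure in the documents is the 87.3% taken to surgery in the EORTC study (section 1.3.1). It is not a rate of timely R0 resection. Used only as an illustration, it gives 0.839 against 0.631.

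**Step 5: size for condition 2.** The same model, with the lower tail.

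| Assumed complication rate | P(X ≤ 6) | P(X ≤ 5) |
|---|---|---|
| 10% | 0.999 | 0.995 |
| 15% | 0.992 | 0.968 |
| 25% | 0.893 | 0.765 |

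The 25% is the postoperative complication rate that section 1.1 cites for the chemotherapy arm. That section does not limit it to serious or drug-attributable events, so it is probably high for this purpose.

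**Step 6: both conditions together, assuming independence.**

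- R0 83%, complications 15%: 0.6749 × 0.9917 = 0.669 by count; 0.4289 × 0.9681 = 0.415 by percentage.
- R0 90%, complications 10%: 0.9174 × 0.9992 = 0.917 by count; 0.7618 × 0.9953 = 0.758 by percentage.

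The joint gaps are 0.669 − 0.415 = 0.254 and 0.917 − 0.758 = 0.159. Condition 1 alone gives 0.246 and 0.156, so nearly all of the gap comes from the R0 cut-off.

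**The case against.** The best defence is that this is a small slip in a soft benchmark. Feasibility is not an objective or endpoint in section 2 or section 8.1. Section 8.4.3 is descriptive and attaches no test or consequence to the criteria, and later cohorts are a Joint Steering Committee decision. A report would show the raw counts, so a reader could see 14 of 17 or 6 of 17 directly. All of this stands, and it limits the weight of the point.

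There is also an innocent explanation. The products 14.11 and 5.61 round to 14 and 6, exactly the printed counts, which is a simpler account than a denominator of 18. It may explain where the mismatch came from, but it does not say which figure governs. Nor does word order settle it. The count comes first in condition 1 and the percentage first in condition 2, so taking the leading figure gives at least 14 and at most 33%. That is an inference the text does not state.

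On the population, section 8.4.1 does assign sets to the R0 rate and to safety, and section 8.4.3 analyses those endpoints. What remains is that a fixed 17 matches neither set by definition. What happens to unresected patients depends on what 17 means, and the documents leave that open. The assumed rates, the independence assumption and n = 17 in the tables are likewise illustrative.

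**Conclusion.** The point holds. Both cut-offs are wrong as written: each count and its percentage differ by one patient, and rounding reconciles neither. The conflict is confined to exactly 14 R0 resections or exactly 6 complications. For the R0 cut-off this is not remote, with a probability of about 0.16 to 0.25 at assumed true rates of 80% to 90% and 17 patients. For the complication cut-off it is small unless the true rate is near 25%. The missing population is a real gap, but its effect cannot be sized from the documents. The benchmark is descriptive, and the primary test and its sample size are not affected.

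**What to change.** Before results are seen, amend section 8.4.3 in two respects.

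- **Make each count agree with its percentage.** If the percentages are intended, the counts become at least 15 and at most 5 of 17. If the counts are intended, the percentages become 82.4% (14/17) and 35.3% (6/17). The choice is the sponsor's.
- **Name the denominator for each criterion**, and say how the cut-off applies if that set does not number 17.

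Optionally, count treated patients who are not resected as failures under condition 1, and report the R0 rate among resected patients separately, as section 8.4.1 already declares.

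The cost is wording only, with no extra data or patients. If the optional change is made, the feasibility figure may be slightly less favourable.

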8.4.4 Exploratory Analysis (or Analysis of Exploratory Endpoints)

Wilcoxon rank-sum test will be used to assess whether there is a relationship between any of the immune cell subsets and objective radiographic response as well as pathologic response. Cox-proportional hazard models will be applied to assess if there is relationship between any of the immune cell subsets and RFS. Parallel analysis will be performed for PD-L1 expression. Wilcoxon rank-sum test will also be used to assess whether the T cell receptor clonality diversity index is different between responders vs. non-responders (defined by objective radiographic response or pathologic response), and between patients who have progression within 1-year vs. those whose disease has not progressed. Additional analyses of immunocorrelative data are detailed in the Lab Manual.

9 Study Management

9.1 Pre-study Documentation

This study will be conducted in accordance with the ethical principles that have their origin in the Declaration of Helsinki as stated in 21 CFR §312.120(c)(4); consistent with GCP and all applicable regulatory requirements.

Before initiating this trial, the Investigator will have written and dated approval from the IRB for the protocol, written ICF, patient recruitment materials, and any other written information to be provided to patients before any protocol related procedures are performed on any patients.

The clinical investigation will not begin until either FDA has determined that the study under the IND is allowed to proceed or the Investigator has received a letter from FDA stating that the study is exempt from IND requirements.

The Investigator must comply with the applicable regulations in Title 21 of the Code of Federal Regulations (21 CFR §50, §54, and §312), GCP/ICH guidelines, and all applicable regulatory requirements. The IRB must comply with the regulations in 21 CFR §56 and applicable regulatory requirements.

9.2 Institutional Review Board Approval

The protocol, the proposed ICF, and all forms of participant information related to the study (e.g. advertisements used to recruit participants) will be reviewed and approved by the UCSF IRB. Prior to obtaining IRB approval, the protocol must be approved by the Helen Diller Family Comprehensive Cancer Center Site Committee and by the Protocol Review Committee (PRC). The initial protocol and all protocol amendments must be approved by the IRB prior to implementation.

9.3 Informed Consent

A signed informed consent form (ICF) and a Health Insurance Portability and Accountability Act (HIPAA) authorization must be obtained before any study-specific assessments are initiated. The investigator or qualified designee will explain the study to the patient and answer all of his/her questions.

All patients must be provided a consent form describing the study with sufficient information for each participant to make an informed decision regarding their participation. Participants must sign the IRB-approved ICF prior to participation in any study specific procedure. The participant must receive a copy of the signed and dated consent document. The original signed copy of the consent document must be retained in the medical record or research file.

All patients who are consented will be registered in OnCore®, the UCSF Helen Diller Family Comprehensive Cancer Center Clinical Trial Management System (CTMS). The system is password protected and meets HIPAA requirements.

9.4 Changes in the Protocol

Once the protocol has been approved by the UCSF IRB, any changes to the protocol must be documented in the form of an amendment. The amendment must be signed by the Investigator and approved by PRC and the IRB prior to implementation.

If it becomes necessary to alter the protocol to eliminate an immediate hazard to patients, an amendment may be implemented prior to IRB approval. In this circumstance, however, the Investigator must then notify the IRB in writing within 5 working days after implementation. The Study Chair and the UCSF study team will be responsible for updating any participating sites.

9.5 Handling and Documentation of Clinical Supplies

The UCSF Principal Investigator and each participating site will maintain complete records showing the receipt, dispensation, return, or other disposition of all investigational drugs. The date, quantity and batch or code number of the drug, and the identification of patients to whom study drug has been dispensed by patient number and initials will be included. The sponsor-investigator will maintain written records of any disposition of the study drug.

The Principal Investigator shall not make the investigational drug available to any individuals other than to qualified study patients. Furthermore, the Principal Investigator will not allow the investigational drug to be used in any manner other than that specified in this protocol.

9.6 Case Report Forms (CRFs)

The Principal Investigator and/or his/her designee, will prepare and maintain adequate and accurate participant case histories with observations and data pertinent to the study. Study specific CRFs will document safety and treatment outcomes for safety monitoring and data analysis. All study data will be entered into OnCore® via standardized CRFs in accordance with the CTMS study calendar, using single data entry with a secure access account. The Clinical Research Coordinator will complete the CRFs as soon as possible upon completion of the study visit; the Investigator will review and approve the completed CRFs.

The information collected on CRFs shall be identical to that appearing in original source documents. Source documents will be found in the patient's medical records maintained by UCSF personnel. All source documentation should be kept in separate research folders for each patient.

In accordance with federal regulations, the Investigator is responsible for the accuracy and authenticity of all clinical and laboratory data entered onto CRFs. The Principal Investigator will approve all completed CRFs to attest that the information contained on the CRFs is true and accurate.

All source documentation and CTMS data will be available for review/monitoring by the UCSF DSMC and regulatory agencies.

The Principal Investigator will be responsible for ensuring the accurate capture of study data. At study completion, when the CRFs have been declared to be complete and accurate, the database will be locked. Any changes to the data entered into the CRFs after that time can only be made by joint written agreement among the Study Chair, the Trial Statistician, and the Protocol Project Manager.

9.7 Oversight and Monitoring Plan

The UCSF Helen Diller Family Comprehensive Cancer Center DSMC will be the monitoring entity for this study. The UCSF DSMC will monitor the study in accordance with the NCI-approved Data and Safety Monitoring Plan (DSMP). The DSMC will routinely review all adverse events and suspected adverse reactions considered “serious”. The DSMC will audit study-related activities to ensure that the study is conducted in accordance with the protocol, local standard operating procedures, FDA regulations, and Good Clinical Practice (GCP). Significant results of the DSMC audit will be communicated to the IRB and the appropriate regulatory authorities at the time of continuing review, or in an expedited fashion, as applicable. See Appendix 2 Data and Safety Monitoring Plan for a Phase 2 or 3 Institutional Study, for additional information.

9.8 Record Keeping and Record Retention

The Principal Investigator is required to maintain adequate records of the disposition of the drug, including dates, quantity, and use by patients, as well as written records of the disposition of the drug when the study ends.

The Principal Investigator is required to prepare and maintain adequate and accurate case histories that record all observations and other data pertinent to the investigation on each individual administered the investigational drug or employed as a control in the investigation. Case histories include the case report forms and supporting data including, for example, signed and dated consent forms and medical records including, for example, progress notes of the physician, the individual's hospital chart(s), and the nurses' notes. The case history for each individual shall document that informed consent was obtained prior to participation in the study.

Study documentation includes all CRFs, data correction forms or queries, source documents, Sponsor-Investigator correspondence, monitoring logs/letters, and regulatory documents (e.g., protocol and amendments, IRB correspondence and approval, signed patient consent forms).

Source documents include all recordings of observations or notations of clinical activities and all reports and records necessary for the evaluation and reconstruction of the clinical research study.

In accordance with FDA regulations, the investigator shall retain records for a period of 2 years following the date a marketing application is approved for the drug for the indication for which it is being investigated; or, if no application is to be filed or if the application is not approved for such indication, until 2 years after the investigation is discontinued and FDA is notified.

9.9 Coordinating Center Documentation of Distribution

It is the responsibility of the Study Chair to maintain adequate files documenting the distribution of study documents as well as their receipt (when possible). The HDFCCC recommends that the Study Chair maintain a correspondence file and log for each segment of distribution (e.g., FDA, drug manufacturer, participating sites, etc.).

Correspondence file: should contain copies (paper or electronic) of all protocol versions, cover letters, amendment outlines (summary of changes), etc., along with distribution documentation and (when available) documentation of receipt.

Correspondence log: should be a brief list of all documents distributed including the date sent, recipient(s), and (if available) a tracking number and date received.

Phase 2, Pembrolizumab, Vactosertib

At a minimum, the Study Chair must keep documentation of when and to whom the protocol, its updates and safety information are distributed.

10 Protection of Human Patients

